2.2 Secondary

- 2.21 To compare the first progression free survival (PFS1) between patients with right sided (primary tumor) metastatic colon cancer who were randomized to receive regorafenib followed by anti-EGFR monoclonal antibody therapy compared to those that receive anti-EGFR monoclonal antibody followed by regorafenib.

- 2.22 To compare the second progression free survival (PFS2) between patients with right sided (primary tumor) metastatic colon cancer who were randomized to receive regorafenib followed by anti-EGFR monoclonal antibody therapy compared to those that receive anti-EGFR monoclonal antibody followed by regorafenib.

- 2.23 To compare the sequential treatment progression free survival (stPFS) between patients with right sided (primary tumor) metastatic colon cancer who were randomized to receive regorafenib followed by anti-EGFR monoclonal antibody therapy compared to those that receive anti-EGFR monoclonal antibody followed by regorafenib.

- 2.24 To assess the frequency and severity of adverse events between patients with right sided (primary tumor) metastatic colon cancer who were randomized to receive regorafenib followed by anti-EGFR monoclonal antibody therapy compared to those that receive anti-EGFR monoclonal antibody followed by regorafenib.

- 2.25 To compare the objective response rate (ORR), while on initial treatment, between patients with right sided (primary tumor) metastatic colon cancer who

were randomized to receive regorafenib followed by anti-EGFR monoclonal antibody therapy compared to those that receive anti-EGFR monoclonal antibody followed by regorafenib.

- 2.26 To compare the objective response rate (ORR), while on sequential treatment, between patients with right sided (primary tumor) metastatic colon cancer who were randomized to receive regorafenib followed by anti-EGFR monoclonal antibody therapy compared to those that receive anti-EGFR monoclonal antibody prior to regorafenib.

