Safety Population: The Safety Population comprises all patients who received any protocol treatment.

- 16.11 **Primary Endpoint:** The primary endpoint is overall survival. The primary objective for this trial is to compare the overall survival (OS) between evaluable patients who were randomized to arm A and arm B. Overall survival is defined as the time from randomization to death from any cause. Patients who are alive at the time of statistical analysis will be censored at the last known alive date.
- 16.12 **Secondary Endpoints:** Each secondary endpoint will be compared between arms. These include first progression free survival (PFS1), second progression free survival two (PFS2), sequential treatment progression free survival (stPFS), objective response rate of initial treatment and sequential treatment, and incidence of adverse events from initial treatment, sequential treatment and whole period.

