16.32 Secondary Endpoints

16.321 First Progression-Free Survival (PFS1)

Progression-free survival one (PFS1) is defined as the time interval between randomization date and the date of first progression while on initial treatment or until death whichever is first, where disease progression will be determined based on RECIST 1.1 criteria. PFS will be estimated using the Kaplan-Meier method and compared between groups using the log-rank test. The median PFS and 95%

confidence interval will be reported. Patients with no defined events observed during the follow-up period will be censored at the last disease assessment date prior to the initiation of sequential treatment, if applicable.

16.322 Second Progression-Free survival (PFS2)

Second progression-free survival (PFS2) is defined as the time interval from re-registration to the sequential treatment phase until the date of progression while on sequential treatment or until death, whichever occurred first. Disease progression will be determined based on RECIST 1.1 criteria. PFS2 will be estimated using the Kaplan-Meier method and compared between groups using the log-rank test. The median PFS2 and 95% confidence interval will be reported. Patients will be censored at the last disease assessment date while on sequential treatment .

16.323 Sequential Treatment Progression-Free Survival (stPFS)

Sequential treatment progression-free survival is defined as the time from randomization until progression while on the sequential treatment or until death, whichever occurred first. Patients who did not experience an event during follow-up will be censored at the last disease assessment date.

Patients who completed initial treatment but did not begin sequential treatment will be censored at the date of last disease evaluation prior to discontinuation of initial treatment. Patients who began sequential treatment but discontinued protocol treatment prior to progression will be censored at the last disease assessment date while on sequential treatment. Analysis methods will mirror those of the other PFS endpoints.

16.324 Objective Response Rate

The objective response rate to initial treatment will be estimated by the number of patients who achieve a best response to initial treatment of complete response or partial response (CR or PR) divided by the total number of evaluable patients. Point estimates and the corresponding 95% confidence intervals for the true success proportions will be calculated.

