16.325 Sequential Treatment Objective Response Rate

The objective response rate to sequential treatment is defined as the number of patients who achieve a best response to sequential treatment of complete response or partial response (CR or PR) while on sequential treatment divided by the total number of evaluable patients who initiated sequential treatment. Point estimates and the corresponding 95% confidence intervals for the true success proportions will be calculated.

16.326 Adverse Events

Adverse events by patient will be summarized by frequencies and severity using CTCAE version 5.0. We will also closely monitor adverse events throughout the study.

16.327 Correlative Research

Serial blood collections – prior to cycle 1, every 8 weeks at the time of restaging scans and disease progression will be collected to post-hoc evaluate for plasma biomarkers prognostic or predictive to response and acquired treatment resistance

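### PFS2 and sequential response are compared between arms only among patients who reach the second drug, a group formed after randomisation, so a difference need not reflect the sequence

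*Combined protocol and SAP*

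**What the plan says.** - **Goals.** Goal 2.22 reads "To compare the second progression free survival (PFS2) between patients with right sided (primary tumor) metastatic colon cancer who were randomized to receive" one sequence or the other. Goal 2.26 uses the same form: "To compare the objective response rate (ORR), while on sequential treatment, between patients with right sided (primary tumor) metastatic colon cancer". They are two of six secondary goals (2.21 to 2.26). Section 16.12 adds: "Each secondary endpoint will be compared between arms".
- **PFS2 (16.322).** "Second progression-free survival (PFS2) is defined as the time interval from re-registration to the sequential treatment phase". A patient who never re-registers has no PFS2. The planned comparison is "PFS2 will be estimated using the Kaplan-Meier method and compared between groups using the log-rank test", with no adjustment.
- **Sequential response (16.325).** Responders are "divided by the total number of evaluable patients who initiated sequential treatment". The analysis is "Point estimates and the corresponding 95% confidence intervals for the true success proportions will be calculated". No test is named.
- **Entry to the second phase.** Section 6.4 allows re-registration within 28 days of documented progression or intolerance. Sections 13.5 and 13.6 leave it to the physician whether the patient re-registers or moves to event monitoring. The test schedules in 4.1 and 4.2 label this registration mandatory, and their footnotes say that patients will be re-registered.
- **stPFS (16.323).** The clock starts at randomisation, but patients who finish drug one and never begin drug two are censored at their last evaluation before stopping drug one.

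The plan attaches no caveat, descriptive label, adjustment or sensitivity analysis to this selection.

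**The concern.** Randomisation makes the arms comparable on the day of randomisation. PFS2 and sequential response use a later subset: patients who came off drug one alive, were fit enough to continue, met the 28-day window and were judged suitable. Drug one is regorafenib in arm A and anti-EGFR therapy with or without irinotecan in arm B, so this filter may act differently in the two arms. If one arm loses more of its frail patients before the switch, its remaining patients will tend to do better on drug two whatever the drug does.

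There is a second problem of interpretation. Drug two is anti-EGFR therapy in arm A and regorafenib in arm B. Even with no selection, PFS2 contrasts two different drugs and does not isolate their order.

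At stake is the reading of two secondary results, one with a p-value, that would be reported as randomised comparisons of the sequences.

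**Working it through.** **1. The plan's own figure.** The documents give no power, alpha or expected number of starters for PFS2 or sequential response, so only the OS design can be reproduced (16.22, 16.23: medians 7.5 and 14.5 months, one-sided 0.1, 80% power).
- Hazard ratio = 7.5/14.5 = 0.517.
- Events (Schoenfeld) = 4 × (1.2816 + 0.8416)² / (ln 0.517)² = 18.03/0.4346 = 41.5, rounded up to 42.
- Critical hazard ratio = exp(−1.2816 × 2/√42) = 0.673. Power at 42 events is 80.4%.

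All agree with the plan. The decision rule in 16.23 uses OS alone.

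**2. Who is in each comparison.**

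| Endpoint | Set | Fixed at randomisation? |
|---|---|---|
| OS, PFS1, initial response | Not restricted to patients reaching drug two | Not selected by crossover |
| PFS2 | Re-registered patients | No |
| Sequential response | Evaluable patients who start drug two | No |
| stPFS | From randomisation; non-starters censored at end of drug one | Time origin yes, censoring no |

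**3. Size for PFS2.** Assumptions, because the plan gives none: 26 per arm; normal frailty with log-hazard coefficient 0.5 to 1.0; fitness correlated 0.5 to 0.7 with (low) frailty and deciding who starts drug two; exponential PFS2 with a 3-month median; no effect of drug or sequence. Hazard ratios are A versus B.

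| Start rates A / B | PFS2 hazard ratio | Two-sided 5% rejection |
|---|---|---|
| Equal | 1.00 | 5-6% |
| 80% / 60% | 1.05-1.13 | 6.0-7.3% |
| 90% / 60% | 1.09-1.20 | 6.4-9.1% |

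At 80%/60% the test rests on about 26 × 0.8 + 26 × 0.6 = 20.8 + 15.6 ≈ 36 patients. With 4,000 replicates, Monte Carlo error near 6.5% is about 1.96 × √(0.065 × 0.935/4000) = 0.8 points. The low end of the 80%/60% range is therefore hardly distinguishable from the no-bias case.

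**4. Direction and mechanism.** A variant with logistic selection, also with no true effect, gave:
- 80%/50%, crossover unrelated to prognosis: 1.00.
- 70% in both arms, selection on prognosis in one arm only: 1.18, rejection 8.9%.
- 90%/50%, moderate to strong selection: 1.17-1.31, rejection 8.0-12.4%.
- 50%/90%, strong selection: 0.80, rejection 9.6%.

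Unequal rates alone do no harm, equal rates do not guarantee safety, and the error can favour either arm.

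**5. Sequential response.** In the 90%/50% runs the starters-only rates were 18.3% versus 21.4% (moderate selection) and 20.8% versus 27.4% (strongest), with no true difference in activity. Over all patients, with non-starters as non-responders, the first pair becomes 0.9 × 18.3 = 16.5% versus 0.5 × 21.4 = 10.7%. The order reverses, because this rate also counts how many patients reached the drug.

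**6. stPFS under the model of step 3.** Two further assumptions: PFS1 median of 3 months and scans every 8 weeks; non-starters are censored as 16.323 directs.

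| Start rates A / B | stPFS hazard ratio | Two-sided 5% rejection |
|---|---|---|
| 80% / 60% | 1.17-1.23 | 8.2-10.8% |
| 90% / 60% | 1.26-1.34 | 11.9-15.5% |

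Non-starters add event-free time during drug one and then leave the risk set, which lowers the apparent hazard in the arm with fewer starters.

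**The case against.** **Consequence is limited.** OS alone drives the decision, and no alpha attaches to PFS2 or sequential response. This stands: it caps the importance of the point but does not make the comparison randomised.

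**Response among patients given a drug is a legitimate quantity, and 16.325 states its denominator openly.** This also stands, as description. Counting non-starters as non-responders answers a different question, so the starters-only rate should be kept beside it.

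**Both endpoints are tested.** A reader might infer this from goal 2.26 and section 16.12. The documents do not support it: a test is named only for PFS2, and 16.325 gives estimates and confidence intervals.

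**The bias is certain, or large.** A reader might infer this from the selection alone. It needs crossover that depends on prognosis and differs by arm in rate or mechanism. The documents give no start rates, and under equal selection the hazard ratio was 1.00. Section 1.4 says that toxicity has limited regorafenib's use and cites 43% and 25% starting a third cycle in a dose-optimisation trial. That makes equal selection an unsafe default, but does not supply crossover rates for this trial.

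**stPFS already gives the clean comparison because it starts at randomisation.** This too is tempting, but the censoring rule in 16.323 depends on the same selection.

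**Re-registration may not be discretionary.** The test schedules call it mandatory, against 13.5 and 13.6. The conflict is real, but loss through death or decline would remain on either reading.

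**Conclusion.** The point holds as a structural one. Goals 2.22 and 2.26 are worded as comparisons of randomised patients, while 16.322 and 16.325 analyse a group formed after randomisation, without a caveat. Only PFS2 carries a planned p-value. The possible distortion is modest in the central case and larger under stronger or one-sided selection; these sizes rest on assumed start rates and selection strengths. The direction cannot be known from the planned analysis. Separately, PFS2 compares different second drugs and does not isolate sequence. The primary OS conclusion is untouched, so this should be corrected but does not threaten the trial's main result.

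**What to change.** - **16.322:** report PFS2 by arm descriptively (Kaplan-Meier curve, median, 95% confidence interval), with no between-arm p-value. Align goal 2.22 and section 16.12.
- **16.325:** add a sequential response rate over all evaluable patients by arm, non-starters counted as non-responders, as the between-arm comparison. Keep the starters-only rate as a description of second-drug activity.
- **Reporting:** give the number starting drug two by arm.
- **stPFS:** do not name it the randomised comparison of the sequence as 16.323 now stands. Leave that role to OS, or first add an analysis that does not censor non-starters at the end of drug one. It could follow them to later progression or death, or count stopping without starting drug two as an event. State that such an analysis mixes start rate with drug activity.
- **Reconcile** 13.5 and 13.6 with the test schedules on whether re-registration is mandatory.

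Cost: wording changes, one fewer p-value and a lower sequential response rate. Sample size and primary analysis do not change. Following non-starters to later progression may need disease-status data beyond the end of drug one; the other changes need no new data.

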13.0 Treatment/Follow-up Decision at Evaluation of Patient

- 13.1 A patient is deemed *ineligible* if after randomization, it is determined that at the time of randomization, the patient did not satisfy each and every eligibility criteria for study entry. The patient may continue treatment off-protocol at the discretion of the physician as long as there are no safety concerns, and the patient was properly registered. The patient will go directly to the event-monitoring phase of the study (or off study, if applicable).
- If the patient received treatment, all data up until the point of confirmation of ineligibility must be submitted. Event monitoring will be required per Section 18.0 of the protocol.
- 13.2 A patient is deemed a *major violation*, if protocol requirements regarding treatment in cycle 1 of the initial therapy are so severely violated that evaluability for the primary endpoint is questionable. All data up until the point of confirmation of a major violation must be submitted. The patient will go directly to the event-monitoring phase of the study. The patient may continue treatment off-protocol at the discretion of the physician as long as there are no safety concerns, and the patient was properly registered. Event monitoring will be required per Section 18.0 of the protocol.
- 13.3 A patient is deemed a *cancel* if he/she is removed from the study for any reason before any study treatment is given. On-study material and the End of Active Treatment/Cancel Notification Form must be submitted. No further data submission is necessary.
- 13.4 Patients who are CR, PR, or SD will continue treatment per protocol with evaluation every 8 weeks, until disease progression or intolerance.
- 13.5 Patients who develop PD while receiving therapy on the initial treatment may be re-registered to the sequential treatment phase, or may go to event-monitoring, per physician discretion. If a patient develops PD while receiving sequential treatment, they will be followed for survival (i.e. event monitoring phase) every 3 months (± 7 days) for 3 years after randomization (per Section 18.0).

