16.31 Primary Endpoint

16.311 Definition

The primary endpoint for this trial is to compare the overall survival (OS) between evaluable patients who were randomized to arm A and arm B. Overall survival is defined as the time from study entry to death from any cause. OS will be estimated using the Kaplan-Meier method and compared between treatment groups using the stratified log-rank test. The median OS and 95% confidence interval will be reported. Patients will be censored at the date patient was last known to be alive.

16.312 Over Accrual

If more than the target number of patients are accrued, the additional evaluable patients will be used for decision making.

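### stPFS (16.323): the censoring sentence for patients who never start sequential treatment makes no exception for death, although the endpoint's definition counts death as an event

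*Combined protocol and SAP*

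**What the plan says.** Section 16.323 of the combined protocol and SAP defines stPFS as "the time from randomization until progression while on the sequential treatment or until death, whichever occurred first". The general censoring sentence follows and is conditional: "Patients who did not experience an event during follow-up will be censored at the last disease assessment date".

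A new paragraph then deals with two subgroups, and neither sentence carries that condition:

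- First, anyone whose initial treatment has ended and who "did not begin sequential treatment will be censored at the date of last disease evaluation prior to discontinuation of initial treatment".
- Second, anyone who started the sequential drug and then "discontinued protocol treatment prior to progression will be censored at the last disease assessment date while on sequential treatment".

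The plan expects non-starters. Under 13.5 and 13.6, patients coming off initial treatment "may be re-registered to the sequential treatment phase, or may go to event-monitoring, per physician discretion". Section 8.6 provides for sequential treatment not following within 28 days, and 16.325 restricts its denominator to patients who did start it. Survival is followed every 3 months up to 3 years after randomization (13.5, 13.6, 18.1), so non-starters' deaths in that period will be in the database.

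**The concern.** Take a patient who stops initial treatment, goes to event monitoring and dies. The definition makes this an stPFS event at death. The non-starter sentence makes it a censored time at a scan taken before initial treatment stopped. The plan does not say which prevails, so two programmers could follow 16.323 and report different event counts.

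Of the three PFS endpoints, stPFS is the only one that covers the whole sequence from randomization. Non-starters are the patients for whom the sequence failed. If they leave the risk set because they stopped and did not cross over, and tend to die soon afterwards, the censoring is related to prognosis and the Kaplan-Meier curve and log-rank test no longer describe the stated endpoint.

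**Working it through.** **The plan's own figures.** There is none for stPFS. The OS design reproduces. With 42 deaths, one-sided alpha 0.1 and HR 7.5/14.5 = 0.517, power = Φ(√42/2 × ln(1/0.517) − 1.2816) = Φ(2.136 − 1.282) = 80.4%, against 80% stated (16.22) and 79.4% simulated (16.24). The critical HR is exp(−2 × 1.2816/√42) = 0.673, as in 16.23. Nothing below alters these.

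**Inputs from the documents.** 26 evaluable patients per arm (16.22); entry at 0.2 per month for 33 months, then 3 per month (16.25), so 0.2 × 33 + 3 × 18 = 60.6; cut-off at 51 + 7.5 = 58.5 months; follow-up capped at 36 months (18.1); scans every 8 weeks (11.1).

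**Inputs assumed.** Exponential times; median 3 months on initial treatment and 3 months to progression on sequential treatment; non-start rates as tabulated; median survival after stopping, for non-starters, of 2 months with a range around it. Deaths during initial treatment are not modelled.

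**Three rules compared by simulation (300,000 patients per arm).**
- *Deaths counted:* every death is an event; living non-starters are followed to cut-off.
- *Literal:* every non-starter is censored at the last scan on initial treatment.
- *Milder:* non-starters who die are events at death; living ones are censored at that scan.

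**Events lost.** At 30% non-starters in each arm there are 0.30 × 52 = 15.6 non-starters. With 2-month survival after stopping, about 46 events per 52 patients occur if deaths count and about 32 on the literal rule: 14/46 = 30% lost. Median stPFS is 6.8 months with deaths counted and 8.1 literally. With 4-month survival it is 7.6 against 8.1, and with 6-month survival 8.1 under both. With 10-month survival the share of events lost falls to 14% at 20% non-starters and 31% at 40%.

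**Between-arm comparison, stPFS HR (A vs B).**

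| Non-starters A vs B | Survival after stopping, months | Deaths counted | Literal | Milder |
|---|---|---|---|---|
| 25% vs 30% | 2 | 0.99 | 1.03 | – |
| 25% vs 35% | 2 | 0.98 | about 1.06 | – |
| 20% vs 40% | 2 | about 0.95 | 1.13 to 1.15 | 0.94 |
| 20% vs 40% | 4 | 1.05 | 1.13 to 1.14 | 1.00 |
| 20% vs 40% | 6 | 1.12 | 1.13 to 1.14 | 1.04 |
| 30% vs 30% | 2 (A), 4 (B) | about 1.15 | 1.00 | – |
| 30% vs 30% | 4 (A), 2 (B) | 0.87 | 1.00 | – |

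The last two rows show that equal non-start rates are no safeguard. When non-starters survive differently by arm, the literal rule hides a difference that the definition would show.

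**Against sampling noise.** At 20% vs 40% and 2 months, the shift is ln(1.13) − ln(0.95) = 0.122 + 0.051 = 0.17 on the log scale. In trials of 26 per arm the SD of the log HR is about 0.39, so the shift is a little under half of one SD. If true stPFS is the same in both arms (3-month survival after stopping) and the test is one-sided at 0.1 (a level assumed here, since none is stated for stPFS), the literal rule favours arm A in 13%, 18% and 23% of trials when non-starters are 30%, 40% and 50% in A against 20% in B. With deaths counted it stays near 10%.

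**Milder rule.** The patients affected are non-starters alive at cut-off. At 30% non-starters that is about 1 of 52 with 2-month survival and about 2 of 52 with 4-month survival. It grows if survival after stopping is long: with a 10-month median and 40% non-starters, about 8 of 52, and median stPFS is 8.2 months against 9.3 with deaths counted and living non-starters followed to cut-off.

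**The case against.** The strongest reply is that the literal reading is not what the authors meant. Section 16.323 has just made death an event and limited censoring to event-free patients, so the next paragraph can be taken as saying only which assessment date applies to two subgroups. The plan's drafting habit supports this. For OS, 16.311 says "Patients will be censored at the date patient was last known to be alive", which taken at its word would censor everyone, while 16.11 shows the intent: "Patients who are alive at the time of statistical analysis will be censored at the last known alive date". PFS2 in 16.322 is equally unqualified: "Patients will be censored at the last disease assessment date while on sequential treatment". This stands. A reader might infer from 16.323 that the sponsor will drop these deaths; the documents do not support that, only that the text permits it.

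The reply does not remove the need for a correction. For OS, 16.11 supplies the missing condition; no section does so for the stPFS subgroups. On the milder reading, a non-starter who dies stays at risk until death while a living one is taken back to a scan on initial treatment, so the censoring date depends on later survival. Any rule that censors at the last assessment has some of this. It is more marked here because survival follow-up can run long after that scan.

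It is also fair that the sizes rest on assumed inputs, that 20% versus 40% is an arbitrary contrast, and that the model is rough: at 30% non-starters it implies a median OS of about 9.8 months, against the plan's 7.5 for arm B. Finally, the non-starter sentence refers to patients who completed initial treatment, so deaths during initial treatment arguably fall outside it and still count.

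**Conclusion.** The concern holds as an unresolved conflict within 16.323 that should be fixed. Confidence is high that the wording is ambiguous and that its literal application gives a wrong result for the endpoint as defined. The size is illustrative. The literal rule loses roughly the non-start share of events when survival after stopping is short. It shifts the hazard ratio noticeably only when non-start rates differ widely or non-starters' survival differs by arm; for gaps of 5 to 10 points in the non-start rate the shift is small. The milder rule usually matters little.

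Two wider inferences are not supported. The primary analysis is not affected: the OS decision rule in 16.23 does not use stPFS. Nor do the documents show that one arm will be favoured, because they give neither a non-start rate nor survival after stopping initial treatment.

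**What to change.** In 16.323:

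1. State that death at any time in follow-up is an stPFS event, whether or not sequential treatment was started or continued.
2. Limit both subgroup sentences (non-starters, and patients who stop sequential treatment before progression) to patients who have not died.
3. For living non-starters, preferably censor at the date last known alive. Death is the only stPFS event still possible for them, so this date does not depend on the outcome. The general sentence must then exempt them, or it would return them to the early scan.
4. Report the number of non-starters by arm.
5. Add a sensitivity analysis that counts first progression as the event for non-starters. In the 20% versus 40% illustration this gives an HR of 0.86, so it answers a different question and should be labelled accordingly.

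Item 3 is a preference. Its small downside is that non-starters' time after first progression counts as event-free in the main analysis; item 5 addresses that. Items 1 and 2 alone resolve the conflict over deaths.

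The cost is wording and minor programming. Survival status is already collected every 3 months, and no new scans or data are needed. The rule should be fixed before stPFS results by arm are seen.
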